12. Ecological Momentary Assessment: Increasingly researchers are recognizing the large degree of variability within the individual, and within the day, and the role this variability has on intervention efficacy. Therefore, ecological momentary assessment (EMA) will be used to study within-person and within-day interactions between sleep quality and duration (assessed via items from the Pittsburgh sleep quality inventory), feeling states (i.e., calmness, fatigue, relaxation, tiredness, assessed via items from the exercise-induced feelings inventory), affect (assessed via the feelings scale), level of hunger (assessed by asking current level of hunger), and craving for food (assessed by asking current craving for favorite meals or snack foods).

Prior to the start of the intervention and following the initial 9-month intervention period, participants will complete week-long daily assessments. These data will align with ActivPAL monitoring. Because data collected via the study EMA website are time-stamped, they will be time-matched to the hourly ActivPAL data. Participants will be instructed to complete assessments upon waking up in the morning and immediately prior to going to bed at night.

Additionally, each participant will receive up to five daily text message prompts with links to secure web-based questionnaires. Each assessment will take the average user less than two minutes to complete, and will contain all items with the exception of sleep items, which will be assessed only during the first assessment of the day.

13. A Technology survey and Intervention survey will be administered at 9 months and 18 months assessment visits to gain insight on the participants opinion of the technology and group dynamic used in this study.

Statistical Analyses

Sample size: The sample size chosen for this study (n=180; 60/group) provides >85% statistical power (with estimated 51 completers per group, see Table) to definitively test our Primary Hypothesis. In our pilot project, the adjusted mean group weight difference after 10 months (5 months of weight loss and 5 months of follow-up) was 3.6 kg (95% CI= 1.2-6.0 kg). Thus, with the longer 18-month time frame in the proposed study, we anticipate there could be a mean group

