The ancillary study to EMPOWER will enable us to acquire baseline brain magnetic resonance imaging (MRI) scans on a random subset of $n = 90$ participants (EMPOWER has a total $n = 160$). We will test the robustness of the brain phenotypes identified in our existing work on an independent cohort, examining how well these phenotypes predict (a) weight loss during the first 6-month intensive phase and (b) weight regain from 6 months to 18 months of follow-up across all three treatment groups, and whether the predictive accuracy is similar between treatment groups. Furthermore, we are leveraging mobile technology in EMPOWER to collect ecological momentary assessment data on patterns of change in appetite, mood, and fatigue throughout the day both at baseline and again at the 6-month assessment following the intensive phase of treatment. A secondary aim of this ancillary study is to examine whether daily fluctuations in appetite, mood, or fatigue mediate the relationship between baseline brain phenotypes and weight loss at 6-months and/or weight regain from 6 to 18 months of follow-up.

Primary Aim: To evaluate the classification accuracy of brain phenotypes based on both structural brain MRI scans and functional brain networks to predict baseline-adjusted weight loss at 6 months and weight regain from 6 to 18 months both as a main effect across the three treatment groups as well as between the three treatment groups.

Secondary Aim: To examine whether the ability of both brain structure and functional brain networks to predict baseline-adjusted weight loss at 6 months and weight regain from 6 to 18 months across the three treatment groups as well as between the three treatment groups can be explained by variation in daily appetite, mood, and fatigue ratings assessed at both baseline and 6-months following the intensive phase of treatment.

Methods and Measures

Our main premise is that the structural features of gray matter and white matter in combination with functional brain networks constitute a brain phenotype for predicting the amount of weight that older adults lose following involvement in the intensive 6-month phase of a weight loss program and the amount of weight regained from 6 months until the 18-month closeout visit. We also hypothesize that the effects of this phenotype on weight loss and weight regain can be explained, in part, by self-regulatory failure due to daily fluctuations in appetite, mood, and fatigue.

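### Appendix A's Secondary Aim lets ratings taken at 6 months explain weight loss already complete by then, so an effect of weight loss on the ratings could be reported as mediation

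*Combined protocol and SAP*

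**What the plan says.** Appendix A (Background, Rationale and Context) names two outcomes to be predicted from a baseline MRI: "weight loss during the first 6-month intensive phase" and "weight regain from 6 months to 18 months of follow-up". Ecological momentary assessment (EMA) of appetite, mood and fatigue is described as collected "throughout the day both at baseline and again at the 6-month assessment following the intensive phase of treatment".

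The same section gives the purpose as to "examine whether daily fluctuations in appetite, mood, or fatigue mediate the relationship between baseline brain phenotypes and weight loss at 6-months"; the sentence goes on to add 6-18 month regain as a joint or alternative outcome. The formal Secondary Aim asks whether prediction of both outcomes "can be explained by variation in daily appetite, mood, and fatigue ratings assessed at both baseline and 6-months following the intensive phase of treatment". The presumed direction is given under Methods and Measures: the phenotype acts in part through "self-regulatory failure due to daily fluctuations in appetite, mood, and fatigue".

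The Data Analysis section of Appendix A covers classification accuracy, sensitivity, specificity, ROC curves and an ANOVA of AUCs. It contains no mediation model, no rule on time order and no check of the reverse direction.

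The main protocol (Study Measure(s), item 12) dates the EMA differently: "Prior to the start of the intervention and following the initial 9-month intervention period, participants will complete week-long daily assessments".

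**The concern.** A mediator has to come before the outcome it is said to transmit. The 0-6 month weight loss is complete at the 6-month visit, and the second set of ratings is taken at that visit or later. An association between those ratings and the loss could mean that the ratings reflect a state that drove the loss, or that the loss changed the ratings. Data in this order cannot separate the two.

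The reverse direction is plausible on the trial's own terms. Aim 3 treats fatigue and appetite as outcomes the interventions may change, and item 8 of the Study Measure(s) plans to examine whether appetite and craving change over the study.

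At stake is the interpretation of the ancillary study. A reverse effect could be taken as support for the appendix's premise that the phenotype works through failure of self-regulation.

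**Working it through.** **Time order**

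| Rating | Against 0-6 month loss | Against 6-18 month regain |
|---|---|---|
| Baseline | before | before |
| 6 months (Appendix A) | after the loss is complete | at the start, in order |
| 9 months (item 12) | 9 - 6 = 3 months after it is complete | 3 months into a window of 18 - 6 = 12 months |

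The Secondary Aim puts the first two rows against both columns. The faulty cell is the 6-month rating against the 0-6 month loss. Under the item 12 schedule that cell is still out of order, and the order for regain is compromised as well.

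**Size, by illustration**

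The documents give no power, effect size or correlation for this aim, so there is no figure of the plan's to reproduce. Inputs: n=90 (Appendix A, Methods and Measures); correlations r1 (phenotype with loss) and r2 (loss with 6-month rating), all assumed. The true model is phenotype to loss to rating, with no effect of the rating on loss. The analysis is a standard product-of-coefficients mediation, declared when both paths have two-sided p<0.05.

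In standardized form:

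- phenotype-to-rating path: a = r1 × r2
- rating-to-loss path given phenotype: b = (r2 - r1 × a) / (1 - a²)
- apparent mediated share = a × b / r1

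Results:

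- r1=0.5, r2=0.5: a=0.25; b=(0.5-0.125)/(1-0.0625)=0.40; share=0.25×0.40/0.5=0.20
- r1=0.3, r2=0.5: a=0.15; b=(0.5-0.045)/(1-0.0225)=0.465; share=0.15×0.465/0.3=0.23
- r1=0.3, r2=0.3: a=0.09; b=(0.3-0.027)/(1-0.0081)=0.275; share=0.09×0.275/0.3=0.08
- r1=0.5, r2=0.2: a=0.10; b=(0.2-0.05)/(1-0.01)=0.152; share=0.10×0.152/0.5=0.03

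The true share is zero in every case.

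Proportion of simulated trials declaring mediation at n=90 (2,000 runs per cell):

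| r1 | r2=0.2 | r2=0.3 | r2=0.4 | r2=0.5 |
|---|---|---|---|---|
| 0.3 | 3.8% | 9.4% | 19.4% | 28.5% |
| 0.5 | 5.4% | 19.3% | 44.4% | 67.6% |
| 0.7 | 7.2% | 27.2% | 63.4% | 90.0% |

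With r1 and r2 both 0.2 the rate is about 3%. If the parent trial's 85% retention applies (90 × 0.85 = 76.5, taken as 76), the 0.5/0.5 rate is about 60%. A Sobel test is more conservative: 58% at 0.5/0.5 and 1% at 0.5/0.2, n=90.

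For comparison, a baseline rating unrelated to phenotype and loss gives false mediation in 0.2-0.4% of runs at n=90.

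**The case against.** **The plan does not pair the 6-month ratings specifically with 6-month loss.** It lists two rating times and two outcomes, and the sensible pairing (baseline ratings with loss, 6-month ratings with regain) is open. This stands in part. A reader might infer that Appendix A relies on 6-month ratings alone to explain the 0-6 month loss; the documents do not support that, because baseline ratings are named in the same sentence. But the sensible pairing is not written down either, and as worded the later ratings are offered for both outcomes.

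**No analysis is specified, so none is wrong.** This stands as to certainty. A reader might infer that false mediation would be reported; the documents support only that it could be. The joint-significance test is an illustration, not the trial's method.

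**The high rates depend on strong correlations.** This stands. At r2=0.2 the rate is at or near 5%. The illustration also treats loss as continuous, while the appendix classifies success and failure. With phenotype and loss both split at the median (an assumption), 67% falls to about 44% at 0.5/0.5, and the 0.3/0.3 rate falls to about 6%.

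**A 6-month rating may stand in for appetite or mood during the loss phase.** This stands too. It would be too strong to say that the constructs cannot lie on the path to weight loss. The defensible statement is that direction is not identifiable from a rating taken when the outcome is complete.

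**This is only the EMA schedule conflict again.** It is not. Choosing either 6 or 9 months leaves the second rating at or after the end of the loss window.

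**Conclusion.** The concern holds in a limited form: one of the four rating-outcome combinations the Secondary Aim permits is out of time order, and nothing in Appendix A excludes it or labels it as associational. The other three are in order with respect to the outcome under Appendix A's own schedule.

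With pure reverse causation at n=90, false mediation ranges from about 3-5% (r2=0.2, r1 from 0.2 to 0.5) to about 67% (both 0.5), and up to 90% at r1=0.7, r2=0.5. The range rests on assumed correlations and an assumed test, so it shows that the problem can be large, not that it will be.

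The consequence is confined to a secondary aim of an optional ancillary study. The parent trial's primary comparison of 18-month weight and its secondary analyses do not use this mediation question. The change is still worth making, because it costs little and the aim carries a causal claim.

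**What to change.** In the Secondary Aim and Data Analysis section of Appendix A:

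1. State that ratings may be tested as mediators only of weight change after the visit at which they are collected.
2. For 6-month weight loss, use baseline ratings.
3. Use the later ratings, or their change from baseline, only for weight change after that visit, adjusted for weight lost up to it. If the second EMA is at 9 months, this means change from 9 to 18 months; body weight is already scheduled at both visits.
4. Report any comparison of end-of-phase ratings with the 0-6 month loss as an association, not as mediation.
5. Note that the baseline ratings and the baseline MRI are both taken before the intervention with no stated order, so the phenotype-to-rating direction is assumed even for baseline ratings.
6. Reconcile the time of the second EMA: 6 months in Appendix A, after 9 months in item 12 of the Study Measure(s). The rule in step 1 works under either.

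The cost is a few sentences and no new data. The downside is that the mediation claim for 6-month loss becomes narrower, resting on baseline ratings only.

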Data analyses: Initial analyses will follow the “intent-to-treat” principle in which data from all randomized participants are analyzed according to their randomized groups. We will document withdrawal and compliance in detail. We will attempt to identify baseline covariates that predict

attrition and compliance, and if such covariates can be identified, the analyses may need to incorporate stratification by these factors to decrease bias. Aim 1 hypothesis will be tested using analysis of covariance (ANCOVA) to compare group differences in 18-mo body weight, adjusted for baseline weight, gender (used to stratify randomization), and treatment arm. Differences in least-squares means and associated 95% confidence intervals will be calculated. Bonferroni adjustment will be used to account for multiple comparisons.

Secondary analyses (Aims 2 & 3)—Hypotheses of Aim 2 secondary outcomes will be tested using ANCOVA with repeated measures, where within subject correlations will be accounted for by using a compound symmetry covariance structure. Differences in least-squares means and associated 95% confidence intervals will be calculated. Group differences in breaks in SB will be tested using a generalized linear model with repeated measures, since a Poisson distribution is a better fit for such count data. Linear regression will be used to examine whether total physical activity energy expenditure and sedentary behavior at 6-months is predictive of less weight regain at 18-months, adjusted for baseline body weight and gender.

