Methods of data acquisition and processing: This project utilizes MRI data acquisition and processing techniques that our laboratory has used for the last decade. In brief, all scans will be performed on a research Siemens 3T Skyra MRI scanner with a 32-channel head coil utilizing our typical imaging protocol. T1 / T2 / FLAIR structural scans, a blood-oxygen-level-dependent (BOLD)-weighted resting scan, and BOLD-weighted trials of food cues and neutral cues will be collected. Diffusion Tensor Images (DTI) and Perfusion Images may also be acquired. The high-resolution (0.98 x 0.98 x 1.0 mm) T1-weighted structural scans will be acquired in the sagittal plane using a single-shot 3D MPRAGE GRAPPA2 sequence (TR = 2.3 seconds, TE = 2.99 ms, 192 slices). Both BOLD-weighted image sequences will be acquired in the axial plane using an echo-planar imaging (EPI) sequence (resolution = 4 x 4 x 4 mm, TR = 2.0 seconds, TE = 25 ms, flip angle = 75°, 35 slices per volume, 160 volumes).

Anatomical Image processing: the T1-weighted structural images will be first segmented into gray matter (GM) and white matter (WM) images using statistical parametric mapping toolbox version 12 (SPM12). Advanced normalization tools (ANTs) will then be used to warp the segmented images to standard space⁸. The warped images will be modulated with the Jacobian deformation field and masked using GM/WM masks provided by the International Consortium for Brain Mapping (<http://www.loni.usc.edu/atlasses>). Finally, the images will be smoothed using ANTs median filter with a radius of 1.5 mm. The resulting images will serve as the inputs into a support vector classifier in order to classify subjects in the low and high weight loss groups.

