Support Vector Machine (SVM) Learning classification: Our recently published SVM model was developed to classify weight loss success and failure in an elderly cohort.¹³ We will apply our published SVM model to the warped GM and WM images from the high resolution structural scans of the participants in the 3 arms of this study, and this SVM will classify the participants into successful and unsuccessful weight loss. In addition, we will apply our more recent machine learning hypergraph model that uses functional brain networks of the resting state and task-based functional brain network data. In addition, we will combine GM and WM images with resting state and task-based fMRI networks in a single machine learning model to compare the performance of this model with the models trained using structural or functional data, alone. We expect that this combined model will enhance prediction accuracy.

Following this EMPOWER clinical trial, we will assess our machine learning models by determining the accuracy, sensitivity, and specificity in classifying the participants' weight loss success/failure. Similar to our published analyses, we will also perform receiver operator characteristic (ROC) analyses to investigate how efficiently the classifiers performed at different decision thresholds. ROC curves plot sensitivity versus '1-specificity' in a given classification decision threshold, and the area under the curve (AUC) is calculated to determine the effectiveness of the predictions and is considered as the best representative score to represent classification algorithm performance. The AUC will be determined for the structural, resting state fMRI brain network, and task-based fMRI networks by themselves, as well as for the analysis combining these datasets in a single model. A one-way repeated measure analysis of variance (ANOVA) will be performed to evaluate for significant differences for the AUC between the 3 types of classifiers.

Human Subject Protection

Subject Recruitment Methods

All study participants will be enrolled in the EMPOWER study and must not have contraindications for an MRI scan. All participants selected for this MRI sub-study will be asked to complete a separate informed consent.

Informed Consent

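### Appendix A gives the brain classifiers no reference model, so a modest above-chance AUC could reflect sex and age rather than a weight-specific brain phenotype.

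*Combined protocol and SAP*

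**What the plan says.** The Primary Aim of Appendix A is "To evaluate the classification accuracy of brain phenotypes based on both structural brain MRI scans and functional brain networks". The phenotypes are to "predict baseline-adjusted weight loss at 6 months and weight regain from 6 to 18 months both as a main effect" across the three arms, and also between arms. The background section of Appendix A adds the question "whether the predictive accuracy is similar between treatment groups".

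Under Anatomical Image processing, gray and white matter images are warped to standard space, modulated with the Jacobian field, masked and smoothed. They then "will serve as the inputs into a support vector classifier in order to classify subjects in the low and high weight loss groups". Under Data Analysis, the models are assessed "by determining the accuracy, sensitivity, and specificity in classifying" weight loss success or failure. AUC is "considered as the best representative score to represent classification algorithm performance". The only test between models is a repeated-measures ANOVA of AUC across the types of brain classifier.

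In Appendix A, sex appears only as a stratum for selecting the 90 participants, and age is not named as a covariate. The Secondary Aim considers only daily appetite, mood and fatigue as explanations. The parent trial, by contrast, compares 18-month body weight "adjusted for baseline weight, gender (used to stratify randomization), and treatment arm". Its secondary analyses list age, race and initial body weight among factors that may influence response (Data analyses).

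**The concern.** The ancillary study asks whether the brain identifies older adults at risk of failing to lose weight. Modulation keeps local tissue volume in the image, so information on head size, and through it sex and age, can reach the classifier. That scans carry sex and age is general reasoning; the documents do not state it. If men and women, or older and younger participants, lose different amounts, a classifier with no weight-specific information will still rank participants better than chance.

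Structural, resting-state and task-based models could all draw on this signal. Comparing them with each other therefore cannot reveal it. A reader of a modest AUC could not tell whether the scan had added anything to what the enrolment form already records.

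**Working it through.** **The reported figures.** Appendix A states no target AUC or power. It does report a previous structural model in 52 people: accuracy 72.62%, AUC 0.82, for the lower versus upper half of weight loss. These are observed results and cannot be rebuilt from design inputs, but they can be checked against each other. Under an equal-variance binormal model, d' = √2 × z(0.82) = 1.295, and accuracy = Φ(1.295/2) = 74.1%. That is 1.5 points from the stated 72.62%, so the pair is consistent.

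**Inputs from the documents.** 90 scanned participants; a recruitment goal of 50% women; ages 65-85; drop-out of no more than 15% in the parent trial, which if it applies here leaves 90 × 0.85 ≈ 76.

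**Assumptions.** Outcome label = upper half of weight loss. Sex difference in weight loss 0.3 to 0.8 SD; age slope 0 to 0.2 SD per SD. The scan encodes sex with AUC 0.95 (separation √2 × z(0.95) = 2.33 SD) and age with correlation 0.7, and holds nothing else about weight.

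**Simulation.** Weight loss = (sex difference) × (±0.5) + (age slope) × age + standard normal error, with 45 women and 45 men and 3,000 studies per setting. The score combines the noisy sex and age signals. The 95% interval is AUC ± 1.96 × the Hanley-McNeil SE. Ideal weights are the true simulated effects; learned weights come from a separate sample of 52.

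| Sex (SD) | Age slope | AUC, sex and age known exactly | Scan score AUC, ideal weights | Interval above 0.5 | Scan score AUC, learned weights | Interval above 0.5 |
|---|---|---|---|---|---|---|
| 0.3 | 0 | 0.56 | 0.55 | 16% | 0.52 | 8% |
| 0.5 | 0.2 | 0.64 | 0.61 | 43% | 0.57 | 29% |
| 0.8 | 0.2 | 0.69 | 0.65 | 73% | 0.62 | 56% |
| 0 | 0 | 0.50 | 0.50 | 3% | 0.50 | 3% |

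Repeat runs differ by one or two percentage points. With 76 participants and ideal weights the shares are about 14%, 40%, 68% and 3%.

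As a check on the threshold, at AUC 0.62 and n = 90 the SE is 0.059. The lower limit is 0.62 − 1.96 × 0.059 = 0.504, so an AUC of about 0.62 is enough to appear better than chance.

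**Accuracy instead of AUC.** At one-sided 0.025 against 50%, the threshold is 55/90 = 61.1%, or 48/76 = 63.2%. If sex and age alone gave a true accuracy of 60%, the threshold is reached with probability 0.46 (n = 90) or 0.33 (n = 76). At 65% the probabilities are 0.81 and 0.68.

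**Wider range.** With sex and age known exactly, a sex difference of 0.25 to 1.0 SD and an age correlation of 0 to 0.3 give AUC 0.55 to 0.75. Scored against the outcome adjusted for sex and age, the same predictor has AUC 0.50.

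**Upper limit of the problem.** An AUC of 0.82 at n = 90 has SE 0.045 and lower limit 0.82 − 1.96 × 0.045 = 0.73. This is above the 0.69 that exact knowledge of sex and age gives in the main settings, though just below the 0.75 at the extreme of the wider range.

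**The case against.** **The documents show no sex or age effect on weight loss.** This stands. Sex is in the Aim 1 model because it stratified randomization, and that outcome is 18-month weight, not loss. The Data analyses section expects the treatments to act similarly in men and women. Age is only a factor that may be evaluated. The effect sizes above are therefore assumptions.

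**Ideal weights are a best case for the problem.** This also stands. Appendix A applies a published structural model developed in 52 people, so the learned-weight columns are closer to the plan, and even those give the model only the two relevant signals.

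**Baseline weight is already handled.** In part. The Primary Aim names baseline-adjusted loss, but Data Analysis does not say how the adjustment enters the success/failure label, and it does not address sex or age.

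**The independent cohort protects the result.** It protects against overfitting, not against a sex or age signal present in both cohorts.

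**The aim is classification accuracy, not added value.** A fair point: replacing the planned measure would change the question. It is a reason to report the gain beside the planned AUC, not instead of it. The published analyses that Appendix A follows may also handle covariates in ways the documents do not show.

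A reader might infer two further faults that the documents do not support. Head motion is not ignored: the BOLD section regresses the six realignment parameters out of each person's functional data. Nor can the scan carry treatment arm, because arm is randomized and imaging precedes the intervention; accuracy is also examined between arms.

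**Conclusion.** The gap is real but narrow. Appendix A plans no reference model, and its comparison among brain classifiers would not reveal a result due to sex and age. This matters for modest AUCs. Whether it occurs depends on sex or age being related to weight loss, on the scan encoding them as strongly as assumed, and on how the classifier weights them; with no such relation, the false signal rate is about 3%.

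A reader might infer that the previous AUC of 0.82 is itself a sex or age artefact, or that any above-chance result here would be uninterpretable. Neither follows: 0.82 exceeds everything that sex and age alone produced across the assumed ranges. The parent trial's analyses are unaffected. This is a cheap improvement to an ancillary analysis.

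**What to change.** Keep the planned accuracy and AUC. In the Data Analysis section of Appendix A, prespecify a reference model for the same outcome in the same participants using sex, age and baseline weight. Include arm as a known predictor of the outcome, not as a confounder of the scan. State how the baseline adjustment enters the success/failure label.

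Report the reference AUC beside each brain model's AUC, and the gain in AUC from adding the brain score to the reference, with a participant-level bootstrap interval. Describe the brain phenotype as adding information beyond routine variables only if the interval for the gain excludes zero. Mean head motion between participants is at most an optional sensitivity covariate for the functional models.

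The cost is a few sentences and one extra model on data already collected. The drawback is that the gain will be smaller than the raw AUC and its interval wide at 90 participants, or about 76 after drop-out.

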Appendix A

Background, Rationale and Context

Although the scientific premise of the EMPOWER Sitless intervention is based on research showing that sedentary behavior in aging has adverse effects on the regulation of body weight^{1,2} and functional decline^{3,4}, recent evidence^{5,6} suggests there will be considerable within-treatment variability in weight loss during the intensive phase of treatment (the first 6-months) and in weight regain from 6- to 18-months. ***For the past six years, we have been investigating whether or not there are brain-based phenotypes among aging adults that place certain individuals at high-risk for failing to lose weight when involved in structured programs of weight loss.*** Indeed, relative to older adults with a low self-reported drive to consume highly palatable foods, their high-scoring counterparts exhibited a shift in brain networks that is typical of other addictive behaviors following exposure to a short-term food restraint.⁷ Most recently, using baseline brain gray and white matter volume within a support vector machine learning model on older adults (n = 52) enrolled in an 18-month weight loss

intervention, we were able to predict classification to the lower or upper half of the weight loss distribution with an average accuracy of 72.62%; a receiver operating characteristic analysis indicated that classification performance was robust based on an area under the curve of 0.82.¹¹ In unpublished work, we have recently used functional network data and have increased prediction accuracy to 93%.

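### Appendix A tests AUC differences between classifiers with a repeated-measures ANOVA but names no replicate unit; a participant-level paired AUC comparison should replace it

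*Combined protocol and SAP*

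**What the plan says.** Under Data Analysis in Appendix A, the published structural classifier is carried over to the new scans ("We will apply our published SVM model to the warped GM and WM images"). A more recent model built on functional networks is also applied. A further model is then built: "we will combine GM and WM images with resting state and task-based fMRI networks in a single machine learning model", in order to "compare the performance of this model with the models trained using structural or functional data, alone".

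Four AUCs are promised. Three are for single sources: "The AUC will be determined for the structural, resting state fMRI brain network, and task-based fMRI networks by themselves". The fourth is for the combined model. The comparison between models is a single sentence: a "one-way repeated measure analysis of variance (ANOVA) will be performed to evaluate for significant differences for the AUC between the 3 types of classifiers".

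Appendix A gives no row unit for this ANOVA, no cross-validation or resampling scheme, no significance level and no power. It does not say on which data the combined model is trained, although its background section states the purpose as "We will test the robustness of the brain phenotypes identified in our existing work on an independent cohort". The Primary Aim has two outcomes, 6-month weight loss and regain from 6 to 18 months.

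**The concern.** A repeated-measures ANOVA needs several rows, each holding one value per classifier. An AUC is a property of a whole cohort, so 90 participants do not supply 90 rows of AUCs. The analyst has to create the rows, and that choice decides whether there is a test, how often it rejects falsely and how much power it has. The p-value for one imaging source outperforming another would rest on a decision that the plan does not record and that could be taken after the data are seen.

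Two linked gaps make the comparison harder to pin down. Four AUCs are listed but three classifier types are tested. These could be structural, functional and combined, or structural, resting-state and task-based; in the second case the combined model is outside the test. Also, a model trained on EMPOWER participants raises a calibration problem that a model applied unchanged does not.

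**Working it through.** The plan gives no figure for this comparison, so there is none to reproduce.

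**Inputs from Appendix A:** 90 scanned participants; three arms; an earlier structural model with AUC 0.82, from a "support vector machine learning model on older adults (n = 52) enrolled in an 18-month weight loss" intervention and predicting the lower or upper half of weight loss.

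**Assumptions, because the documents are silent:** 45/45 outcome split; 30 participants per arm; binormal scores with AUC = Φ(μ/√2); score correlation between classifiers 0 to 0.7; two-sided 5% level; all 90 with outcomes.

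**1. Degrees of freedom.** For k classifiers and r rows, error df = (k − 1)(r − 1).
- One AUC per classifier: (3 − 1)(1 − 1) = 0, so F is undefined.
- Three arms: 2 × 2 = 4.
- Five folds: 2 × 4 = 8.

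**2. False positives, equal true AUCs, models applied unchanged** (simulated, 1,500 to 4,000 cohorts per setting; ranges are over settings with AUC 0.70 to 0.82 and different correlations and splits).
- Single-pass five folds as rows: 4.0-7.7%.
- Three arms as rows: 4.4-7.4%.
- Paired DeLong test, 2 df, on participants: about 4-6%.
- Ten bootstrap resamples as rows: about 70% or more in most settings (lowest 67%).

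Resamples fail because they share the same 90 participants. The ANOVA error term then measures resampling noise, not the variation from drawing a new cohort.

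**3. Power, models applied unchanged.** The lower end of each range is correlation 0, the upper end 0.7.

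| True AUCs | DeLong | 5-fold ANOVA | 3-arm ANOVA |
|---|---|---|---|
| 0.72/0.72/0.82 | 32-72% | 19-46% | 16-36% |
| 0.72/0.72/0.87 | 70-99% | 44-84% | 31-65% |

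More folds narrow the gap without closing it. For the first row at correlation 0.3, nine folds give 26%, five folds 23% and DeLong 39%.

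**4. Participant as the unit.** An ANOVA on jackknife pseudovalues, one per participant and classifier, had type I error of 4.2-5.4%. At correlation 0.4 its power was 41% against 46% for DeLong (first row) and 82% against 86% (second row).

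**5. Models trained on EMPOWER.** With ridge classifiers cross-validated inside the cohort and equal expected AUCs, false positives over the feature sets tried were 7-22% for DeLong on out-of-fold scores and 7-20% for the single-pass fold ANOVA. Neither holds 5%. For models fitted on 52 earlier participants and applied unchanged to 90, the DeLong 95% interval covered the true difference in 93-95% of cohorts.

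**6. Interval width.** At AUC 0.82 and correlation 0.4 the standard error of a difference is 0.0503, so the half-width is 1.96 × 0.0503 = 0.099. At correlation 0.7 it is 1.96 × 0.037 = 0.073, and at 0 it is 1.96 × 0.062 = 0.122. If 15% are lost by 18 months, the rate in the protocol's Sample size section, 90 × 0.85 = 76.5 remain for regain. The middle value becomes 0.099 × √(90/76.5) = 0.107.

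**The case against.** The strongest reply is that the planned sentence can be carried out validly. Disjoint folds or arms hold about 5%, and pseudovalues give a valid repeated-measures ANOVA nearly as powerful as DeLong. That is correct. It means the ANOVA is not wrong under every reading, and the power loss applies to fold or arm rows, not to every valid unit. The pseudovalue analysis is itself a participant-level paired comparison, though, and the plan does not mention it.

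A reader might infer that the plan will use resamples as rows and so have a grossly inflated error rate. The documents do not support that: no resampling scheme is proposed, and carrying existing models over suggests one score per participant. Inflation is a risk the wording leaves open.

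A reader might also infer that DeLong repairs the whole comparison. It does not. For a combined model trained on EMPOWER it is no better calibrated than the fold ANOVA.

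Finally, the cited earlier analysis may define the unit. Appendix A refers to published work for its ROC analyses, not for the ANOVA, and does not reproduce the method. This point cannot be settled from the documents, and it is one reason for low severity.

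**Conclusion.** The concern holds in a limited form. The plan names a test without its replicate unit. On the literal reading there is no test; with fold or arm rows and models applied unchanged, the test is valid but clearly weaker than a paired comparison on participants. The zero degrees of freedom follow from arithmetic alone. The sizes of the power loss and of the possible inflation rest on the assumed AUCs, score correlations, outcome split and row schemes; DeLong had more power than fold or arm rows in every setting tried.

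Severity is low. Comparing models is in neither aim of the ancillary study. A reader might take the point to undermine its classification-accuracy aim or the trial's body-weight analysis; neither uses this ANOVA, and neither is affected.

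**What to change.** Replace the ANOVA sentence with a participant-level paired comparison of correlated AUCs (DeLong, or a bootstrap that resamples participants), using one out-of-sample score per participant per model. Report each AUC difference with its 95% confidence interval.

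State also:
- Whether the three types are structural, functional and combined, or structural, resting-state and task-based, and the contrasts that follow.
- Holm adjustment over the contrasts actually tested, for each outcome (6-month loss, 6-to-18-month regain).
- The data on which each model is trained. P-values are given only for models fitted and locked before EMPOWER outcomes are used. For any model trained or tuned on EMPOWER, including the combined model if that applies, the difference and interval are descriptive.

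The cost for models applied unchanged is appendix wording and a few lines of code, with no extra scans or participants. The intervals will be about ±0.10 with 90 participants, and wider for regain if about 15% drop out. Locking the combined model needs earlier data holding every scan type, which the documents do not confirm, and a model fitted on a smaller cohort may predict less well. Without such data, the combined-model contrast has no p-value.
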